4. SUBJECT SELECTION CRITERIA

The Investigator should keep a record, the volunteer screening log, of volunteers who entered pre-study screening.

Each volunteer should meet all of the inclusion criteria and none of the exclusion criteria for this study. Under no circumstances can there be exceptions to this rule.

4.1 Inclusion criteria

For inclusion in the study volunteers should fulfill the following criteria:

Provision of informed consent prior to any study-specific procedures

1. Healthy male and/or female volunteers between the ages of 18 to 75 years, inclusive, with veins on the back of both hands and both forearms suitable for cannulation or repeated venipuncture. For Part A, volunteers must be willing to have both arms used during the study with catheters inserted for up to a maximum of 72 hours (6 infusions).
2. Women of childbearing potential must have a negative pregnancy test (at screening and at each admission), be nonlactating, be using a highly-effective form of birth control for 1 month before enrollment (confirmed by the Investigator), and be willing to use a highly-effective form of birth control during the study and until 3 months after their last dose of IP. Women of nonchildbearing potential must fulfill 1 of the following criteria:
 - Postmenopausal, defined as amenorrhea for at least 12 months following cessation of all exogenous hormonal treatments and with follicle stimulating hormone (FSH) levels in the laboratory-defined postmenopausal range

- Have documentation of irreversible surgical sterilization by hysterectomy, bilateral oophorectomy, or bilateral salpingectomy (but excluding tubal occlusion) at least 12 months prior to screening
- 3. Male volunteers must be willing to use barrier contraception ie, condoms, from the first day of dosing until 3 months after the last dose of IP.
- 4. Have a body mass index (BMI) between 18 and 30 kg/m², inclusive, and weigh at least 50 kg
- 5. As judged by the Investigator, able to understand and be willing to communicate with the Investigator and comply with all the study requirements

4.2 Exclusion criteria

Volunteers should not enter the study if any of the following exclusion criteria are fulfilled:

1. Involvement in the planning and/or conduct of the study (applies to AstraZeneca, Cerexa, Forest employees, their close relatives, and/or staff at the study site)
2. Previous randomization to treatment sequence in the present study
3. Use of any other investigational compound or participation in another clinical trial, within 3 months prior to first administration of IP in this study. The period of exclusion begins at the time of the last visit of the prior study. Volunteers consented and screened but not dosed in this study or previous Phase I studies are not excluded.
4. History of any clinically significant disease or disorder, eg, cardiac, neurological, hematological, psychiatric, gastrointestinal, hepatic, renal disease, or other condition which, in the opinion of the Investigator, may either put the volunteer at risk because of participation in the study, or influence the results or the volunteer's ability to participate in the study
5. History or presence of gastrointestinal, hepatic, or renal disease or any other condition known to interfere with the absorption, distribution, metabolism, or excretion of drugs
6. Any clinically significant illness, medical/surgical procedure, or trauma within 4 weeks of the first administration of IP
7. Any clinically significant abnormalities in the physical examination, laboratory values, or 12-lead ECG, as judged by the Investigator
8. Abnormal vital signs, after 10 minutes supine rest, defined as any of the following:

- Systolic blood pressure >140 mm Hg
 - Diastolic blood pressure >90 mm Hg
9. Any positive serology result on screening for serum hepatitis B surface antigen (HBsAg), hepatitis C antibody (HCV), or human immunodeficiency virus (HIV)
 10. Known or suspected history of drug abuse, as judged by the Investigator
 11. Current smokers or those who have smoked or used nicotine products within the previous 3 months
 12. History of alcohol abuse or excessive intake of alcohol, as judged by the Investigator
 13. Positive screen for drugs of abuse, or smokerlyzer test at screening or positive screen for drugs of abuse, alcohol breath test or smokerlyzer test on admission to the unit prior to the first administration of IP
 14. History of severe allergy/hypersensitivity or ongoing allergy/hypersensitivity, as judged by the Investigator, or history of any hypersensitivity or allergic reaction to any β -lactam antimicrobials or drugs with a similar chemical structure or class as ceftaroline
 15. Excessive intake of caffeine- or xanthine-containing foods or beverages, eg, coffee, tea, caffeine-containing energy drinks, and cola (more than 5 cups of coffee or equivalent per day)
 16. Use of any prescribed or nonprescribed medication including antacids, analgesics (other than paracetamol/acetaminophen or hormone replacement therapy), herbal remedies, vitamins, and minerals during the 2 weeks prior to the first administration of IP or longer if the medication has a long half-life. Occasional use of paracetamol/acetaminophen is allowed for minor pains and headache.
 17. For Part B, plasma donation, or any blood donation, blood product donation, or blood loss greater than 500 mL during the 3 months prior to screening
 18. Creatinine clearance of less than 80 mL/minute (Cockcroft-Gault Formula)

$$\text{Males : } CrCL(\text{mL} / \text{min}) = \frac{(140 - \text{age}) \times (\text{kg body weight})}{(0.814 \times \text{micromol} / \text{L serum creatinine})}$$

$$\text{Females : } CrCL(\text{mL} / \text{min}) = \frac{(140 - \text{age}) \times (\text{kg body weight}) \times 0.85}{(0.814 \times \text{micromol} / \text{L serum creatinine})}$$

Where age is expressed in years, weight in kg, and serum creatinine in mg/dL

19. Judgement by the Investigator that the volunteer should not participate in the study if they have any ongoing or recent (ie, during the screening period) minor medical complaints that may interfere with the interpretation of study data or are considered unlikely to comply with study procedures.

Procedures for withdrawal of incorrectly-enrolled volunteers are presented in Section 5.3.

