At the clinical dosages of ceftaroline fosamil studied (600 mg iv every 12 hours or 400 mg iv every 12 hours given as 60-minute infusions), ceftaroline demonstrated an acceptable safety profile that was compatible with treatment of cSSSI and CABP. In addition, no safety concerns were identified in the safety review beyond those already known to be cephalosporin class effects.

The cumulative clinical experience with ceftaroline identified the following adverse reactions:

Table 1 Reported adverse events that may be related to ceftaroline (by System Organ Class)

System Organ Class	Adverse events
Blood and lymphatic disorders	Thrombocytopenia, anemia
Nervous system disorders	Headache, dizziness
Gastrointestinal disorders	Diarrhea, nausea, vomiting, abdominal pain
Skin and subcutaneous tissue disorders	Rash, pruritus, urticaria
Vascular disorders	Phlebitis
Immune system disorders	Hypersensitivity or anaphylaxis
Infections and infestations	Clostridium difficile colitis
Investigations	Increased blood creatinine and transaminases, prolonged prothrombin time, international normalized ratio increased, positive direct Coombs
General disorders and administrative site conditions	Infusion site reactions, erythema, pain, phlebitis, pyrexia

This information appears in Table 10-1 of the Investigator Brochure.

The following is a summary of the basic pharmacokinetic (PK) properties of ceftaroline (following iv infusion of ceftaroline fosamil), based on in vitro and in vivo data:

- Rapid conversion of the prodrug, ceftaroline fosamil, by phosphatases to active ceftaroline in plasma
- Low human plasma protein binding (approximately 20%) of ceftaroline with no distribution into erythrocytes
- Maximum plasma concentration (C_{max}) and area under the plasma concentration-time curve increase approximately proportionally to dose (50 to 1000 mg), with a terminal half-life ($t_{1/2}$) of 2 to 3 hours
- Metabolized by opening of ceftaroline's β -lactam ring to ceftaroline, the microbiologically inactive metabolite M-1, and additional minor unidentified metabolites
- No inhibition or induction of cytochrome P450 (CYP450) isoenzymes in vitro
- No metabolism by CYP450 isoenzymes in vitro
- No accumulation or time-dependent PK observed after repeated doses every 12 hours

- Eliminated mainly through renal excretion (clearance is approximately equivalent to the glomerular filtration rate)

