6.3.6 Laboratory safety assessment

Blood and urine samples for determination of clinical chemistry, hematology, and urinalysis will be taken at the times indicated in the study plan (see [Table 2](#) and [Table 3](#)). The date and time of collection of all laboratory tests will be recorded in the appropriate CRF. Volunteers will fast for 4 hours prior to the clinical laboratory evaluations. Laboratory variables to be measured are shown in Table 6.

Table 6 Safety laboratory variables

Haematology	Clinical chemistry	Urinalysis
Blood (B)-hemoglobin	Serum (S)-albumin	Urine (U)-glucose
B-platelet count	S-alanine aminotransferase	U-hemoglobin
B-absolute leukocyte differential count ^a	S-aspartate aminotransferase	U-protein
B-leukocyte count	S-alkaline phosphatase	Microscopic examination ^b
B-reticulocytes	S-bilirubin, total	
B-erythrocytes	S-calcium, total	
B-hematocrit	S-creatinine	
B-erythrocyte mean cellular volume	S-glucose	
	S-potassium	
	S-sodium	
	S-total protein	

^a The leukocyte differential count will include: neutrophils, eosinophils, basophils, lymphocytes, and monocytes.

^b All urine samples will be evaluated microscopically.

Creatinine clearance will be estimated using the Cockcroft-Gault formula (see [Section 4.2](#)) at screening and at clinic discharge on Day 4 of Period 2 for Part A and Day 4 for Part B.

Additionally, at screening all volunteers will be tested for HIV, HBsAg, and antibodies to HCV. If indicated for females, FSH will be measured to determine their menopausal status at screening. Urine will be tested for drugs of abuse at screening and admission to the study

center on Day -1 including amphetamines, barbiturates, tricyclic antidepressants, cocaine, methadone, phencyclidine, tetrahydrocannabinoid, benzodiazepines, and opiates. For female volunteers a serum pregnancy test will be performed at screening and a urine test on each admission to the study center (Day -1).

Alcohol breath test and smokerlyzer test will be conducted at screening and admission. Laboratory values outside the reference limit suspected to be of any clinical significance will be repeated. Volunteers in whom suspected values of clinical significance are confirmed will either not be included in the study or, if already randomized, will be followed until normalization or for as long as the Investigator considers necessary. Additional laboratory assessments may be performed for safety reasons if judged appropriate by the Investigator.

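### Exclusion criterion 18 names two creatinine units: the equations use micromol/L, the legend beneath them says mg/dL, and following the legend would overstate clearance about 88-fold

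*Supplement*

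**What the plan says.** Criterion 18 in Section 4.2 (Exclusion criteria) of the protocol as amended excludes volunteers with "Creatinine clearance of less than 80 mL/minute (Cockcroft-Gault Formula"). It then prints one equation for men and one for women. The numerator is 140 minus age, times body weight, with a further factor of 0.85 for women. The denominator of both is 0.814 times serum creatinine, and it carries its own unit label: "0.814 \times \text{micromol} / \text{L serum creatinine" (typesetting marks as they appear in the extracted text). The line directly below gives a different unit: "Where age is expressed in years, weight in kg, and serum creatinine in mg/dL".

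Section 6.3.6 relies on the same equations. It says "Creatinine clearance will be estimated using the Cockcroft-Gault formula", refers back to Section 4.2, and sets the times as "at screening and at clinic discharge on Day 4 of Period 2 for Part A and Day 4 for Part B". It also says that safety samples go to the local laboratory of the study center. The reporting unit for creatinine is not stated there or elsewhere.

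Section 4 allows no exceptions to the selection criteria.

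**The concern.** A user who reads the equation enters micromol/L. A user who reads the legend enters mg/dL. The numerical value differs by a factor of about 88 between the two, so this is not a matter of rounding or style, and nothing else in the protocol settles which unit applies.

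The variable matters for this drug. Section 1.1 describes ceftaroline as "Eliminated mainly through renal excretion (clearance is approximately equivalent to the glomerular filtration rate"). The study admits "Healthy male and/or female volunteers between the ages of 18 to 75 years, inclusive", with the further condition that they "weigh at least 50 kg". At the older and lighter end of that range, an unremarkable creatinine can go with a clearance well under 80 mL/min, so the calculation itself is the safeguard. If the legend governed, a volunteer whom criterion 18 is meant to exclude could be randomized. In Part B, which needs only about 8 evaluable volunteers, one such person could move the descriptive summaries of exposure.

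**Working it through.** **Inputs from the protocol.** Threshold 80 mL/min, constant 0.814, factor 0.85 for women, and the two conflicting units (all Section 4.2, criterion 18). Maximum age 75 years and minimum weight 50 kg (Section 4.1).

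**Assumptions from outside the protocol.** 1 mg/dL of creatinine = 88.4 micromol/L, and the mg/dL form of Cockcroft-Gault has the constant 72.

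**Step 1: which unit does 0.814 belong to?** 72 / 88.4 = 0.8145, and in reverse 0.814 × 88.4 = 71.96. The printed constant is the micromol/L constant and agrees with the unit label inside the equations. The legend is the odd one out.

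**Step 2: size of the error if the legend is followed.** Age, weight and sex cancel. The ratio of the two results is the ratio of the two creatinine values, 88.4 for every volunteer.

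**Step 3: worked cases**, with clearance = (140 − age) × weight × (0.85 if female) / (0.814 × creatinine).

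| Illustrative volunteer | Creatinine | micromol/L entered | mg/dL entered |
|---|---|---|---|
| Man, 70 y, 60 kg | 132.6 micromol/L = 1.5 mg/dL | 4200 / 107.94 = 38.9 (excluded) | 4200 / 1.221 = 3440 (passes) |
| Woman, 75 y, 50 kg | 88.4 micromol/L = 1.0 mg/dL | 2762.5 / 71.96 = 38.4 (excluded) | 2762.5 / 0.814 = 3394 (passes) |
| Man, 30 y, 70 kg | 88.4 micromol/L = 1.0 mg/dL | 7700 / 71.96 = 107.0 (passes) | 7700 / 0.814 = 9459 (passes) |

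**Step 4: could the exclusion trigger on the legend's reading?** A computed value below 80 would need a true clearance below 80 / 88.4 = 0.9 mL/min. The lowest numerator among eligible volunteers is at 75 years and 50 kg. Creatinine would have to exceed 2762.5 / (0.814 × 80) = 42 mg/dL for a woman, or 3250 / (0.814 × 80) = 50 mg/dL for a man. In practice the exclusion could not trigger.

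**Step 5: the other reading.** With micromol/L, the first two volunteers are excluded and the third passes, so the criterion works.

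**The case against.** A reader might infer that the protocol instructs the site to use mg/dL and so has switched off its renal exclusion. The documents do not support that. The unit micromol/L is printed in both equations and mg/dL appears once, beneath them. Anyone who enters the unit named in the equation gets the right answer. Because the laboratory's reporting unit is not given, neither reading can be called the one in use. The wrong reading also produces clearances in the thousands, which a screening physician would probably question. These points stand, and they make the harm conditional. They do not remove the contradiction: an implausible result may alert staff, but the page would still give them two units.

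A second argument is that criterion 18 is not the only protection. Criteria 4 and 5 exclude renal disease, criterion 7 excludes clinically significant laboratory abnormalities, and Section 6.3.6 repeats out-of-range values suspected of clinical significance. This also stands in part. Those rules might well catch the 70-year-old man with creatinine 1.5 mg/dL. They would not reliably catch the 75-year-old, 50 kg woman with creatinine 1.0 mg/dL, whose low clearance shows only when it is calculated.

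Third, the downstream effects are limited. A reader might infer that the discharge estimate or the Part B comparison would be spoiled. The discharge clearance feeds no stated decision rule, and Section 12.2.3 names no summary of it. In Part B each volunteer receives both infusion volumes, and Section 11.2 calculates individual ratios of the lower volume to 250 mL. A volunteer's low clearance acts in both periods and largely cancels in those ratios. Only the absolute summaries by treatment are exposed. Section 1.1 also says that mild renal impairment needs no dose adjustment, so volunteers just under 80 mL/min matter less than the worked cases near 38 to 39 mL/min.

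**Conclusion.** The contradiction is real, stands in the current text, and sits in an eligibility rule that allows no exceptions. The legend is the faulty part. That conclusion rests on the two stated assumptions (88.4 micromol/L per mg/dL, and 72 for the mg/dL form) and on the unit label inside the equations, which agrees with it.

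The size is conditional. If a mg/dL value is entered, clearance is overstated 88.4-fold for everyone and the exclusion below 80 mL/min cannot trigger. If a micromol/L value is entered, there is no error. The documents do not show which unit the site used, so the finding is an inconsistent specification and not evidence that anyone was wrongly enrolled. The 80 mL/min threshold is not in question. The correction should be made because the rule depends on this calculation and the remaining exclusions cover only part of the gap.

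**What to change.** In Section 4.2, criterion 18, change the creatinine unit in the legend from mg/dL to micromol/L. Leave both equations and the 80 mL/min threshold as they are. Section 6.3.6 refers back to Section 4.2, so it needs no separate edit.

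Then check the unit in which the local laboratory reports creatinine and the unit that the site's calculation sheet expects. If any clearances have already been calculated, look for values in the thousands and recalculate them.

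The cost is a change to one unit in the protocol text and one check at a single center. No analysis, sample size or visit changes.

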5. STUDY CONDUCT

5.1 Restrictions during the study

The following restrictions apply for the specified times during the study period:

1. Fast for at least 4 hours prior to clinical laboratory evaluations
2. Eat and drink only the standardized meals and drinks provided (apart from water) during the residential periods in the unit
3. Abstain from consuming any of the following:
 - Alcohol from 72 hours before admission to the clinic, during each residential period, and for 72 hours before the study follow-up visit
 - Energy drinks containing taurine or glucuronolactone, eg, Red Bull from 72 hours before admission, during each residential period, and for 72 hours before the study follow-up visit
 - Caffeine- and xanthine-containing food and drink from 48 hours prior to infusion of the first dose and during each residential period, apart from any provided as part of a standardized meal. Excessive intake of caffeine should be avoided during the washout period (Part A) and between discharge from the unit and the study follow-up visit.
 - Poppy seeds found in specialty breads from time of consent until after the final medical examination at the study follow-up visit
4. Abstain from nicotine use, smoking, and drugs of abuse from time of consent until after the final medical examination at the study follow-up visit
5. Abstain from taking any medication, prescribed or over-the-counter products (other than paracetamol/acetaminophen or hormone replacement therapy), from 2 weeks prior to the first administration of IP until after the final medical examination at study follow-up visit. However, this should not obviate necessary medical treatment. If any medication is necessary during the residential period, it should be prescribed by the Investigator and the AstraZeneca Clinical Pharmacology Alliance (CPA) Physician should be informed.

6. Volunteers should refrain from strenuous physical activity, which is not within the volunteers' normal daily routine, from 7 days prior to first admission to the unit until after the final medical examination at the study follow-up visit
7. Volunteers participating in Part B of the study should abstain from blood or plasma donation from 3 months before screening until 3 months after screening
8. Male volunteers should use a condom to prevent pregnancy and drug exposure of a partner and refrain from donating sperm or fathering a child from the date of dosing until 3 months after dosing with the IP; female partners of male volunteers must use another form of highly effective contraception from the time the male volunteer receives the first dose until 3 months after the last dose. Women of childbearing potential must be using a highly-effective form of birth control for 1 month before enrollment (confirmed by the Investigator), and be willing to use a highly-effective form of birth control during the study and until 3 months after their last dose of IP.
9. Remain in the unit during each residential period until all study assessments and procedures have been completed including completion of the 72-hour infusions (sixth final infusion set in Period 2) for Part A and collection of the 24-hour PK sample for Part B

5.2 Subject enrollment and randomization

The Investigator will:

1. Obtain signed informed consent from the potential volunteer before any study-specific procedures are performed
2. Assign potential volunteer a unique enrollment number, beginning with 'E0001001'
3. Determine volunteer eligibility. See Sections [4.1](#) and [4.2](#).
4. Assign eligible volunteers a unique subject number, beginning with '1001'

If a volunteer withdraws from participation in the study, then his/her enrollment/randomization code cannot be reused.

Procedures for randomization

Randomization schemes will be produced for each study part separately by using the global randomization system. Randomization will be performed on Day 1 just before administration of the IP. Randomization codes will be assigned strictly sequentially as volunteers become eligible for randomization.

For Part A, volunteers will be randomly assigned in a 1:1 fashion to 1 of 2 treatment sequences (to Sequence 1 or 2 or, in the event the 50-mL infusion volume is deemed poorly tolerated, to Sequence 3 or 4) of infusion volumes of ceftaroline fosamil 600 mg and placebo,

as outlined in Table 4 (see Section 3.1.1). These sequences avoid administering active treatment in the same arm for both treatment periods and administering the same volume to both arms within the same treatment period.

Table 4 Treatment arm randomization scheme

Sequence	Crossover period	Left arm	Right arm
Sequence 1	1	50 mL active (Treatment A)	250 mL placebo (Treatment D)
	2	50 mL placebo (Treatment B)	250 mL active (Treatment C)
Sequence 2	1	250 mL active (Treatment C)	50 mL placebo (Treatment B)
	2	250 mL placebo (Treatment D)	50 mL active (Treatment A)
Sequence 3	1	100 mL active (Treatment E)	250 mL placebo (Treatment D)
	2	100 mL placebo (Treatment F)	250 mL active (Treatment C)
Sequence 4	1	250 mL active (Treatment C)	100 mL placebo (Treatment F)
	2	250 mL placebo (Treatment D)	100 mL active (Treatment E)

Sequence 3 and Sequence 4 are conditional, as described in Section 3.1.1.

For Part B volunteers will be randomly assigned in a 1:1 fashion to either treatment sequence CA or AC. If Treatment A is shown to be poorly tolerated in Part A of the study, Treatment E will replace Treatment A in Part B, and the volunteers will be randomized 1:1 to treatment sequence CE or EC. The arm infused will switch from the first period to the second and thus the randomization will be stratified by the ordering of infusion (RL and LR), to balance any potential arm effects, and to avoid confounding arm with period effects.

